PracticeGround: Transforming Training and Delivery of Mental Health EBPs

NCT02314624 | Patient Protocol | October 18, 2017

Patient Study Process overview

1. [Initial Phone Call](#)
2. [Review Screen](#)
3. [Informed Consent Call](#)
4. [Action Steps after Informed Consent Call](#)
5. (collect this date from therapist) [Welcome/Get to Know you Session](#)
6. [Scheduling Call](#)
7. [Logging Scheduling Call into Tracking DB](#)
8. [Mental Health Services Satisfaction Survey \(MSSS\)](#)
9. [Assessment Calls](#)

PI Cell Phone Numbers:

[name]: [contact]

[name]: [contact]

Step 1: Set Up Time for Initial Phone Call

1. Review clinic procedures and notes in the [Summative Tracking DB](#). Ensure they are associated with a clinic and make note of their referring provider (if indicated). If needed, find out the patient's medical record number from the referring clinic and log this in the tracking database along with the patient's name.
2. Open the [Eligibility Screen DB](#). Ensure the client is entered into the Client Referral tab.
3. Call the patient to let them know about the study and gauge their interest in participation.
4. Open the [Eligibility Screen on SurveyMonkey](#) in case patient prefers to complete screen with you over the phone.

Voice-mail Script:

Hi! This is _____ from Evidence-Based Practice Institute. I'm calling to tell you more about the research study you talked with the folks at <>Agency<> about. I would love to talk more with you about the study! I will also send you more information by email after I leave this message. Please reply to that email or call me at (phone #) when you have a few minutes to talk. Thank you!

If they call you back or pick up

Hello _____. My name is _____ and I'm calling from Evidence-Based Practice Institute. I'm calling to tell you more about the study and see if you might be interested in participating. I expect this call will take about 15 minutes. Is now a good time to talk?

WILLOW Full RCT Patient Protocol

If it is, proceed.

If not, schedule a time to call back later. Log call time and date in the Pilot RCT Calendar.

We at the Evidence-Based Practice Institute are conducting a research study to test two different approaches to the treatment of depression. We have developed a new software system called WILLOW that assists therapists in providing treatment for depression. We are interested in learning whether computers can be used to help therapists treat patients experiencing depression, whether it is helpful in reducing a patient's depression, and how patients feel about the use of computers to help in their care.

This study compares two different approaches to the treatment of depression. One approach is called "standard care" which involves a therapist applying their usual treatment strategies to treat your depression. In most cases, computers are not used. The other treatment condition is called "computer-assisted therapy" which involves the use of the new computer tool we developed that was designed to help therapists deliver evidence based treatment. If you are eligible and decide to participate, we will ask that you meet weekly with your research therapist for 12 weeks. Over the course of the study, we will ask that you complete 4 sets of study surveys online and over the phone. You will earn up to \$140 for your participation in the study.

Does this sound like something you might be interested in?

If no, thank them for their time and hang up.

If yes, proceed to the next section.

Awesome! Do you have any questions for me?

Great! The next step would be for you to complete a survey to see if you meet the requirements for the study. I expect the survey to take about 15 minutes. Would you like to complete this survey over the phone with me now or would you prefer to complete it online on your own? If I send you the survey after we hang up, will you have time to complete it today?

If patient prefers to complete survey over the phone:

Read each set of instructions and the following questions to the patient verbatim. Click their answers in SurveyMonkey as you go.

Once all questions are answered:

1. [Thank participant, let them know we will follow up soon about eligibility and next steps.](#)

If patient prefers to complete survey online:

Great! I will send you an email shortly that contains the link to the survey and we ask that you complete it within the next two days. After you complete the survey, we will contact you again to talk with you about next steps.

WILLOW Full RCT Patient Protocol

Thank you so much for your interest in our research. Please don't hesitate to contact us if you have any questions as you are filling out the survey. Have a great day!

Step 2: Review Screen

1. Check Survey Monkey for screen if it is your folder day
 - a. **Screen:**
https://www.surveymonkey.com/collect/?sm=rdfeMF4WmHZAwsLTT7mCDtxNhHMMd_2B_2BgRbeMWz3R_2Bz1Oyx9qXYlgLMacO5axHRWS
 - b. Click on **Exports** on the left hand side of the screen
 - c. Click **Export All** and choose **All Responses Data** in the dropdown
 - d. Select .XLS for format
 - e. In the **Cells**: dropdown menu choose "Numerical Value"
 - f. Click the **Export** button
 - g. When it finishes loading, click the drop down arrow and select download.
 - h. Open the zip file
 - i. Go to excel folder and select Sheet_1
 - j. Copy and paste answers into 'PatientScreen.ALL' tab in the [Eligibility Screen DB](#)
 - k. Score PHQ-9 to ensure patient meets criteria for depression (Total score = 11+). See column AQ in 'PatientScreen.ALL' tab in the [Eligibility Screen DB](#) for total score.
 - l. Determine if patient is eligible or not.
 - i. If eligible: copy/paste information into 'Eligible.Patients' tab in [Eligibility Screen DB](#)
 - ii. If unsure: consult with [name] on how to follow up
 - m. Review screen for any skipped questions or those you need to follow-up on. Note these as follow-up items during phone call.
 - n. Review 'Patient Referrals Received' tab in the [Eligibility Screen DB](#)
 - i. If they are not listed in the list, look to see what clinic they are from in the screen to ensure they are being treated at one of our participating clinics
 - o. **Make note if they gave us permission to contact their therapist and/or clinic**

If patient is ineligible:

1. Send ineligible email
2. If we have permission to contact therapist and/or clinic, call to inform the clinic that patient is ineligible to participate

If patient passes screen or unsure:

1. Flag any questions and consult with [name] on how to answer.

WILLOW Full RCT Patient Protocol

2. Create a cover sheet for the patient with contact information and keep notes of all interaction with the patient in the log.
3. Call and Email Patient for clarification of eligibility and/or Informed Consent

Voicemail Script if Eligible:

Hi this is _____ from Evidence-Based Practice Institute. I'm calling to let you know that you are eligible to participate in our study! The next step to enroll in this study is to read and sign the consent form and take your first set of study surveys. I will send you more information about this process via email after I leave this message. Please reply to that email or call me at (phone #) to schedule a time for these next steps. Thank you!

Voicemail Script if Follow-up Needed to Determine Eligibility:

Hi this is _____ from Evidence-Based Practice Institute. I'm calling to talk with you more about your participation in our study. We just have a couple of questions about the answers you provided in the online questionnaire. I will also send you an email after leaving this voicemail message. Please reply to that email or call me back at (phone #) at your earliest convenience. Thank you!

1. If they call you back
 - a. And it is a good time for you to talk: Go through the script below
 - b. And it is not a good time for you to talk: Schedule a time you can call them back.
 - i. Log call time and date in the Research Calendar
 - c. Log the call in the cover sheet
2. If they pick up, use the script below in Step 2.

~~~~~

### **Step 3: Patient Informed Consent Call**

Hi, is this \_\_\_\_\_?

Hello \_\_\_\_\_, my name is \_\_\_\_\_ and I'm calling from Evidence-Based Practice Institute. I am calling to let you know that based on the answers you provided on the online survey, you are eligible to participate in the study! The next steps for your participation in this study is for me to tell you more about the details of the study and then there are a couple of things for you to complete online. I expect this entire process to take about 1-1.5 hours. Is now a good time for this or would you like to schedule another day this week or early next week for this?

**If it is, proceed to the next section.**

**If not, schedule a time to call back later.**

Great! I want to start off by telling you a little bit about the study. We are studying different treatments for depression. This study will compare two approaches to treating depression –

## WILLOW Full RCT Patient Protocol

standard therapy and computer-assisted therapy aided by our newly developed software called WILLOW. If you decide to participate in this study, you will be asked to meet with a therapist for 12 weeks. Your therapist has already been assigned to one of the two study conditions [let them know what condition they were assigned], which means you are also in the [standard care, WILLOW] condition with them.

**<<for RA: if not yet assigned to therapist, describe both conditions. If assigned to therapist and we know their condition, describe only the condition they are assigned to unless they want to hear about both conditions.>>**

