### **Describe CAU:**

Since you are assigned to a therapist in the standard therapy condition, you will receive their standard therapy for treating depression. This means your therapist will be using their usual method for treating depression with you. This condition is sometimes called “care as usual”. If you have any questions about the specifics of your sessions and therapy, please direct those to your therapist.

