### **Describe WILLOW:**

Since you are assigned to a therapist in the computer-assisted therapy condition, your therapist will be using WILLOW to help provide you treatment for your depression. In this condition, your therapist will be using WILLOW to help provide an evidence-based treatment known as Behavioral Activation. WILLOW also includes a number of videos, worksheets, and discussion guides your therapist may choose to use.

Do you have any questions so far?

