**If there are no questions, move on to the next section**

### **Describe Surveys:**

Four times during the 12-week study you will be asked to complete some questionnaires online.

- The first time will be today after we finish with our call. I will be sending you the links to our online consent form and also the link to the first set of surveys for you to do.
- As a kind of addendum to today's surveys, I'll also be sending you a link to a really quick survey for you to do after your next session.

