**If there are no questions, move on to the next section**

Participation in this study is completely voluntary. You can decline at any time if you are not interested in participating.

Now that you know a more about the study, are you still interested in participating? Do you have any questions?

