## WILLOW Full RCT Patient Protocol

**If yes, continue with the script**

**If no, thank them for considering the study and end call**

**Describe next steps:**

Okay, I'd like to summarize the next steps for us now. I will send you the link to our online consent form for you to complete after this call.

- It will review the information we just discussed and also provide you with more details about participating in this study.
- The survey will also include more information about The Health Insurance Portability and Accountability Act (HIPAA)

After you're done with the consent form, the survey will direct you back to the email I'll be sending to you in a minute. There will be another link in the email that will take you to the first set of surveys. We expect that they will take about 30-45 minutes to complete. This survey will ask for your study ID, if you have something to write on I can provide that right now? Or I can text it to you if that's better for you. Which do you prefer?

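### On the consent call, patients with a known study therapist learn their arm before consent and baseline, and the recruitment instructions to therapists conflict, so consent and, where therapists recruit, case mix can depend on arm

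*Protocol*

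**What the plan says.** **Order of events for therapists.** Therapists are randomised after their own consent (Therapist Protocol, Steps 2 to 5). They are told their condition on the warm call (Step 6) and only later become ready to accept study patients (Step 9).

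**Order of events for patients.** In the Patient Protocol, Step 3, the script opens by naming both approaches and then says "Your therapist has already been assigned to one of the two study conditions [let them know what condition they were assigned". Staff are instructed, for a patient whose therapist's condition is known, to "describe only the condition they are assigned to unless they want to hear about both conditions". The two arm-specific texts begin "Since you are assigned to a therapist in the standard therapy condition" and "Since you are assigned to a therapist in the computer-assisted therapy condition". Later in the same call comes "Now that you know a more about the study, are you still interested in participating". Consent follows: "I will send you the link to our online consent form for you to complete after this call". The self-report baseline follows that: "The first time will be today after we finish with our call" and "There will be another link in the email that will take you to the first set of surveys". A patient not yet assigned to a therapist hears both conditions described.

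**Recruitment text.** In the Therapist Protocol, Step 7, Standard Care therapists are told that the clinic will assign their study patients. WILLOW therapists are told that patients come from the clinic or through their own recruiting. The Step 9 script is headed for both conditions. It has the therapist pick patients likely to be interested and hold a welcome discussion, named after WILLOW, before referring them. Step 2 requires patients to be new to the clinic and not previously treated by that therapist. Step 9, however, speaks of finding them on the therapist's caseload, and the Step 12 script allows for a client who has attended the clinic before.

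**Analysis.** The SAP (Analysis Strategy) takes Time by Condition as the effect of interest where there is a baseline, and Condition where an outcome is measured only at follow-up. It reports no statistically significant baseline differences.

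**The concern.** Patients enter after their therapist has been randomised and knows the arm. Randomising therapists therefore does not by itself make the patients in the two arms comparable. That depends on patients being found, approached and consented in the same way in both arms.

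The call script lets the decision to join depend on the arm. A patient told that the therapist will provide usual care, and one told that the therapist will use a new tool, are not deciding about the same offer. The recruitment text may let the source of patients differ by arm as well. Either would mix the effect of WILLOW with differences in who was enrolled, for every outcome. A lesser issue is that the baseline questionnaires are answered by patients who already know their arm.

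**Working it through.** **1. Who is affected by the disclosure.** Only patients who already have a therapist of known condition at the consent call. Step 4 of the Patient Protocol builds the patient ID from the therapist ID and keeps a separate number series for unassigned patients, so both routes were foreseen. The share on each route is not stated.

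**2. What the recruitment texts imply for case mix.**

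| Reading | Can case mix depend on arm? |
|---|---|
| Clinics assign all patients in both arms | Only if clinics act on the therapist's arm, which is not documented |
| Clinics assign in Standard Care; clinics assign or therapists recruit in WILLOW (Step 7 taken literally) | Yes, because the source differs by arm |
| Therapists in both arms choose whom to refer (Step 9) | Yes, because the person choosing knows the arm |

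The Patient Protocol, Step 1, also records a clinic or provider referral route. The documents do not say which route was used, in which arm, or how often.

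**3. Baseline reporting.** No figure in the documents can be reproduced here, so the following is an illustration on assumptions. Suppose that knowing the arm shifts self-reports by d between arms at baseline and by r·d at follow-up, and that a share p of patients is told on the call. The absolute contribution of the told patients to the Time by Condition contrast is then:

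- disclosure before baseline (as written): p(1 − r)d
- disclosure just after baseline: p·r·d, because these patients still know their arm at Weeks 4, 8 and 12

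With d = 0.2 SD and p = 1:

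| r | As written | Disclosure after baseline |
|---|---|---|
| 0 | 0.20 SD | 0 |
| 0.5 | 0.10 SD | 0.10 SD |
| 1 | 0 | 0.20 SD |

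With p = 0.5 each entry halves. The two expressions are equal at r = 0.5. Moving the disclosure lowers this contribution only when r is below 0.5 and raises it when r is above. This takes the follow-up shift as unaffected by when the patient is told.

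**4. Outcomes measured only at follow-up.** They do not use baseline, so the shift in step 3 at baseline cannot reach them. Differential consent, case mix and arm-aware reporting at follow-up all can.

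**5. What the SAP's baseline comparison can exclude.** The SAP gives no number of patients, estimate or interval. For a true difference of 0.2 SD, a two-sided 5% test has SE = √(2/n) for n patients per arm:

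- n = 30: SE 0.258, power about 12%
- n = 50: SE 0.200, power about 17%
- n = 100: SE 0.141, power about 29%

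These n are assumed and clustering is ignored. The figures show only what such a test can detect from any cause; they do not measure this bias. Even a well-powered test would not address differential consent or unmeasured case mix.

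**The case against.** The strongest reply is that telling a patient a known allocation is a defensible choice in an open trial that randomises therapists. That stands, and it limits the severity. Consent from unassigned patients who do not know their arm is only a partial precedent, because for them there is no allocation to withhold.

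There are also real safeguards. The first staff call describes both approaches, the consent call opens by naming both, and any patient may ask to hear both described. A PHQ-9 screen (total of 11 or more) precedes the consent call, and the exclusion criteria are the same in both arms. The consent form itself is not in the documents and may describe both conditions. These reduce the problem. None of them controls what is disclosed before the decision to join, or how patients are sourced in each arm.

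A further reply is that later disclosure would not cure arm-aware reporting. That is right, as step 3 of the working shows. The case for moving it therefore rests on consent and selection.

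Finally, the SAP is written in the past tense, so a script change may come too late. For patients already enrolled only reporting remains.

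**Conclusion.** The point holds as a risk of arm-dependent consent and, where therapists recruit, of arm-dependent case mix. Arm-aware baseline reporting is secondary. Size and direction cannot be computed, because the documents give no sample size, no share of patients told and no consent counts by arm. All values of d, r, p and n above are assumptions. Severity is modest, and the improvement is cheap.

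A reader might infer more than the documents support:

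- *That the results are biased.* The texts show that bias is possible, not that it occurred.
- *That every patient was told the arm.* Unassigned patients hear both conditions.
- *That case mix depends on arm whoever assigns patients.* If clinics assign everyone, this needs clinics to act on the arm, which is not documented.
- *That naming the arm after baseline removes reporting bias.* It does so only if none of the shift persists to follow-up.
- *That the absence of significant baseline differences settles the matter.* It does not, for the reasons in step 5.

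**What to change.** **Any future enrolment.**

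- Give every patient the neutral description of both conditions on the consent call. Remove the sentence disclosing the arm, the instruction to describe one condition only, the openings of the two arm-specific texts, and the WILLOW-specific insert later in the Step 3 script.
- Tell patients on that call that they will learn their arm after consent and baseline. Name it on a call after baseline and before the first study session. The existing call-back can serve, with staff placing the call if the patient does not.
- Reconcile the recruitment wording in the Therapist Protocol, Steps 2, 7, 9, 12 and 16, into one statement identical in both arms, including who counts as a new patient. Give the welcome discussion a neutral name.

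**Patients already enrolled.**

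- From the existing logs, report by arm the numbers referred, screened, consented, excluded at intake and analysed under the SAP's five-session rule. Report also the share with a therapist of known condition at the consent call.
- Give baseline and screening PHQ-9 estimates with intervals by arm, for all consented patients as well as the analysed set, since the five-session rule selects after assignment. Note that the screening score is truncated at 11 and may itself follow a discussion with the therapist.
- State the order of disclosure and the recruitment route as limitations.

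**Cost.** The prospective part is a few script edits and one call. Staff briefly withhold an allocation they know, and a few patients may withdraw on learning it. The gain is partial, because some patients learn the arm from the therapist first: Step 9 places the welcome discussion before referral, and the Patient Protocol, Step 5, notes that some clinics hold the welcome session before mentioning the study. The reporting part is a flow table, a baseline table and a short limitation statement.

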### **Describe CAU:**

Since you are assigned to a therapist in the standard therapy condition, you will receive their standard therapy for treating depression. This means your therapist will be using their usual method for treating depression with you. This condition is sometimes called “care as usual”. If you have any questions about the specifics of your sessions and therapy, please direct those to your therapist.

### **Describe WILLOW:**

Since you are assigned to a therapist in the computer-assisted therapy condition, your therapist will be using WILLOW to help provide you treatment for your depression. In this condition, your therapist will be using WILLOW to help provide an evidence-based treatment known as Behavioral Activation. WILLOW also includes a number of videos, worksheets, and discussion guides your therapist may choose to use.

Do you have any questions so far?

**If there are no questions, move on to the next section**

### **Describe Surveys:**

Four times during the 12-week study you will be asked to complete some questionnaires online.

- The first time will be today after we finish with our call. I will be sending you the links to our online consent form and also the link to the first set of surveys for you to do.
- As a kind of addendum to today's surveys, I'll also be sending you a link to a really quick survey for you to do after your next session.

